## LIST OF ABBREVIATIONS AND RELEVANT DEFINITIONS

AE	Adverse Event
CRF	Case Report Form
DSMB	Data Safety Monitoring Board
DTF	Desmoid-type fibromatosis
EORTC	European Organisation for Research and Treatment of Cancer
EORTC QLQ-C30	European Organisation for Research and Treatment of Cancer, Quality of Life Questionnaire-Core-30
EQ-5D-5L	EuroQoL 5 dimensions, 5 levels
EudraCT	European drug regulatory affairs Clinical Trials
FAP	Familial Adenomatous Polyposis
GCP	Good Clinical Practice
GDPR	General Data Protection Regulation; in Dutch: Algemene Verordening Gegevensbescherming (AVG)
HRQoL	Health-related quality of life
IC	Informed Consent
IQR	Interquartile range
METC	Medical research ethics committee (MREC); in Dutch: medisch-ethische toetsingscommissie (METC)
MC	Medical Center
PROFILES	Patient Reported Outcomes Following Initial treatment and Long term Evaluation of Survivorship
QoL	Quality of Life
(S)AE	(Serious) Adverse Event
SD	Standard Deviation
Sponsor	The sponsor is the party that commissions the organisation or performance of the research, for example a pharmaceutical company, academic hospital, scientific organisation or investigator. A party that provides funding for a study but does not commission it is not regarded as the sponsor, but referred to as a subsidising party.
SUSAR	Suspected Unexpected Serious Adverse Reaction
VAS	Visual Analogue Scale
WGBO	Dutch Medical Treatment Contracts Act; in Dutch: Wet op de Geneeskundige Behandelingsovereenkomst
WMO	Medical Research Involving Human Subjects Act; in Dutch: Wet Medisch-wetenschappelijk Onderzoek met Mensen

## **SUMMARY**

**Rationale:** Desmoid-type fibromatosis (DTF) is a rare, histologically benign soft tissue tumour. Although incapable of metastasizing, the clinical course is unpredictable and can be aggressive because of local invasive growth. Many invasive treatments (i.e. surgery, chemotherapy, radiotherapy) may be considered in patients with symptomatic disease but unfortunately, these 'traditional' treatment options do not guarantee tumour reduction and/or clinical response. Local recurrence after surgery remains high. Active surveillance is now recommended as a first line management for most patients with DTF. Therefore, DTF has obtained a more 'chronic' status and its impact on patients should be evaluated accordingly.

Health-related quality of life (HRQoL) provides information beyond traditional measures of efficacy in oncology such as overall survival, and is increasingly used as an endpoint in clinical trials. Based on previous studies we concluded that there is currently no HRQoL measure suitable for DTF patients. Additionally, we concluded that few is known about the quality of life of patients living with this rare disease. The previous studies led to the development of a DTF-specific HRQoL questionnaire named the 'DTF-QoL'.

By obtaining data from a relatively large group of patients with this rare disease, we will be able to evaluate the prevalence of HRQoL problems in adult DTF patients. The hypothesis is that patients with DTF have issues on several HRQoL domains including physical, social and emotional well-being. This study aims to evaluate HRQoL issues experienced by DTF patients.

### **Objective:**

The primary objective is to evaluate HRQoL problems in adult DTF patients.

The secondary objectives are:

1. To compare the level of HRQoL of DTF patients to the general population.
2. To identify patient subgroups who are at risk for developing certain HRQoL problems,
3. To evaluate patient preferences regarding their health care needs for DTF.

**Study design:** Multicentre, cross-sectional, observational, cohort study.

### **Study population:**

All patients, aged 18 years and above with a histopathological proven DTF and sufficient Dutch language skills who have received their last check-up at a medical oncologist or surgical oncologist specialized in DTF, in the hospital within the last five years (between October 2014 and October 2019).

**Intervention (if applicable):** Eligible patients will be asked to fill out a set of questionnaires consisting of 173 questions in total. Patients will only have to fill out these questionnaires once.

### **Main study parameters/endpoints:**

To evaluate HRQoL problems in adult DTF patients, regardless of their disease stage or treatment course, using the DTF-QoL, the EORTC QLQ-C30, and the EQ-5D-5L questionnaires.

Secondary objectives:

- a) Comparison of EORTC QLQ-C30 scores (describing symptoms, single items, functioning and global health) between DTF patients and the general population (age- and sex-matched).
- b) Identification of DTF patients who are at risk for impaired HRQoL (risk factors).
- c) Evaluating patient preferences for the health care for DTF.

**Nature and extent of the burden and risks associated with participation, benefit and group relatedness:**

The total number of questions is 173.

Completing all the questionnaires will take about 30-60 minutes. Our experience of high response in previous large-scale cancer survivorship studies using the PROFILES (Patient Reported Outcomes Following Initial treatment and Long term Evaluation of Survivorship) registry indicates that this number of questionnaires and its content is feasible and well accepted by patients. However some patients might find this burdensome. Risks are considered to be negligible and the burden is considered to be minimal. Because patients will complete these questionnaire in their own time, they will have the time and space to think about HRQoL issues which are important to them.

## **1. INTRODUCTION AND RATIONALE**

Desmoid-type fibromatosis (DTF) is a benign soft tissue tumour which can cause significant morbidity by local aggressive growth behaviour. Due to its local aggressive behaviour, and its known tendency of local recurrence after initial surgical resection, it is categorized as a borderline tumour in clinical guidelines. This tumour is rare with an estimated incidence of 5 patients per million persons per year in the Dutch population. The biological behaviour is variable with phases of progressive growth, growth stabilization and even regression of the tumour without any treatment. Most patients are females, aged between 20 and 40 years at primary diagnosis.

Sporadic DTF arises in musculoaponeurotic structures with the most common sites being the abdominal wall and the extremities. Symptoms vary, depending on tumour site, size and infiltration of adjacent structures, resulting in pain and/or functional impairment. DTF does not metastasize, and rarely has fatal outcomes. Surgical resection, radiotherapy, non-cytotoxic and cytotoxic systemic therapies may be considered in patients with symptomatic disease but unfortunately, these 'traditional' treatment options do not guarantee tumour reduction and/or clinical response. Local recurrence after surgery remains high, leading to a reduction in surgical treatments for DTF over recent decades. Additionally, 'active' forms of treatment can be debilitating, causing greater morbidity than the tumour itself. For these reasons, active surveillance is now recommended as a first line management for most patients with DTF. Therefore, DTF has obtained a 'chronic' status and its impact on patients should be evaluated accordingly.

Health-related quality of life (HRQoL) provides information beyond traditional measures of efficacy in oncology such as overall survival, and is increasingly used as an endpoint in clinical trials. We previously performed a systematic literature review to evaluate which HRQoL-measures were used in research to assess HRQoL in DTF. Studies used generic HRQoL-measures (e.g. the cancer specific core questionnaire from European Organisation for Research and Treatment of Cancer; the EORTC quality of life core questionnaire (EORTC QLQ-C30)), which may not consider disease-specific issues in DTF patients. Also, site-specific tools (e.g. Toronto Extremity Salvage Score), were used, which may not be relevant to certain groups (e.g. those with an abdominal wall, or head and neck tumours).

At present, there is no validated DTF-specific HRQoL-tool. In order to gain greater insight into the issues that patients with DTF experience in their daily lives, and to evaluate their experiences with the current health care and supportive system for DTF, we previously organised focus groups and semi-structured interviews, in the United Kingdom and in the Netherlands. These studies identified issues covering various domains including; the diagnostic pathway, the treatment pathway, daily limitations (e.g. physical and psychological symptoms), and experiences with the current health care system. Additionally, issues were ranked according to their relevance by patients and health care providers ([name] et al., 2019, submitted). A DTF-specific HRQoL tool, named the DTF-QoL, was developed based on the results of these studies.

With the current study we would like to assess the HRQoL problems experienced by DTF patients. The DTF-specific tool, the (DTF-QoL), combined with additional HRQoL-tools will be used to gain more insight into the problems that DTF patients face on a daily basis. This study functions as an exploratory study which may generate new hypotheses for future studies.

## **2. OBJECTIVES**

Primary objective: To evaluate HRQoL problems in adult DTF patients, regardless of their disease stage or treatment course, using the DTF-QoL, the EORTC QLQ-C30, and the EQ-5D-5L questionnaires.

Secondary objectives:

1. To compare the level of HRQoL of DTF patients to that of the general population (age- and sex-matched), using the EORTC QLQ-C30 (version 3.0).
2. To identify DTF patients who are at risk for late effects and/or impaired HRQoL (risk factors), using the baseline questionnaire, the DTF-QoL (version 1.0), the EORTC QLQ-C30 (version 3.0), and the EQ-5D-5L (version 1.0).
3. To evaluate patient preferences regarding their health care for DTF, using the healthcare utility and decision making questionnaires (both version 1.0).

### **3. STUDY DESIGN**

Multicentre, cross-sectional, observational, cohort study.

### **4. STUDY POPULATION**

#### **4.1 Population (base)**

Patients, aged  $\geq 18$  years, diagnosed with a histopathological proven DTF, regardless of disease stage and received treatment(s) who have received their last check-up of their DTF in one of the participating hospitals the hospital between October 2014 and October 2019.

#### **4.2 Inclusion criteria**

In order to be eligible to participate in this study, a subject must meet all of the following criteria:

- Patients, aged  $\geq 18$  years
- Patients with histopathological proven DTF, regardless of disease stage or treatment.
- Patients diagnosed between January 1990 and October 2019, with a visit to the hospital for their DTF (between October 2014 and October 2019)
- Patients with sufficient Dutch language skills
- Patients competent to complete a questionnaire
- Patients with a written informed consent

#### **4.3 Exclusion criteria**

A potential subject who meets any of the following criteria will be excluded from participation in this study:

- Patients diagnosed with familial adenomatous polyposis (FAP)

#### **4.4 Sample size calculation**

The incidence of DTF is 5.4 patients per million per year. However, a sample size calculation is challenging due to rarity of the disease and lack of published data regarding this subject. In our previous study, the response rate of the Dutch patients was 41.5%. The Erasmus MC pathology database from 1990 until 2019 contains roughly 250 patients. Since we are a tertiary academic centre, about one third of these patients are pathology consultations from other centres. A small fraction of the remaining patients will be excluded because they are younger than 18 years old (about 5%) and because their desmoid tumour is part of the genetic syndrome Familial Adenomatous Polyposis (FAP) (about 5%). Because of the high incidence of malignant colorectal tumours in FAP patients, these patients might experience different HRQoL problems compared to patients with "sporadic" DTF. Currently, there are about 80 patients who are under follow-up at our institution. With the participation of two other centres with similar patient numbers we hope to approach a total of 250 patients. Based on the previous response rate we expect to obtain data from 100 DTF patients.

### **5. TREATMENT OF SUBJECTS**

Not applicable, as this study does not involve an investigational product.

**5.1 Investigational product/treatment**

Not applicable, as this study does not involve an investigational product.

**5.2 Use of co-intervention (if applicable)**

Not applicable, as this study does not involve an investigational product.

**5.3 Escape medication (if applicable)**

Not applicable, as this study does not involve an investigational product.

**6. INVESTIGATIONAL PRODUCT**

Not applicable, as this study does not involve an investigational product.

**6.1 Name and description of investigational product(s)**

Not applicable, as this study does not involve an investigational product.

**6.2 Summary of findings from non-clinical studies**

Not applicable, as this study does not involve an investigational product.

**6.3 Summary of findings from clinical studies**

Not applicable, as this study does not involve an investigational product.

**6.4 Summary of known and potential risks and benefits**

Not applicable, as this study does not involve an investigational product.

**6.5 Description and justification of route of administration and dosage**

Not applicable, as this study does not involve an investigational product.

**6.6 Dosages, dosage modifications and method of administration**

Not applicable, as this study does not involve an investigational product.

**6.7 Preparation and labelling of Investigational Medicinal Product**

Not applicable, as this study does not involve an investigational product.

**6.8 Drug accountability**

Not applicable, as this study does not involve an investigational product.

**7. NON-INVESTIGATIONAL PRODUCT**

Not applicable, as this study does not involve a non-investigational product.

**7.1 Name and description of non-investigational product(s)**

Not applicable, as this study does not involve a non-investigational product

**7.2 Summary of findings from non-clinical studies**

Not applicable, as this study does not involve a non-investigational product

**7.3 Summary of findings from clinical studies**

Not applicable, as this study does not involve a non-investigational product

**7.4 Summary of known and potential risks and benefits**

Not applicable, as this study does not involve a non-investigational product

**7.5 Description and justification of route of administration and dosage**

Not applicable, as this study does not involve a non-investigational product

**7.6 Dosages, dosage modifications and method of administration**

Not applicable, as this study does not involve a non-investigational product

**7.7 Preparation and labelling of Non Investigational Medicinal Product**

Not applicable, as this study does not involve a non-investigational product

**7.8 Drug accountability**

Not applicable, as this study does not involve a non-investigational product

## 8. METHODS

### 8.1 Study parameters/endpoints

#### 8.1.1 Main study parameter/endpoint

The EORTC QLQ-C30 (version 3.0) questionnaire, the DTF-QoL questionnaire, and the EQ-5D-5L questionnaire will be used. More information about these questionnaires can be found in Appendix 1.

The mean score or median score per scale of the EORTC QLQ-C30 questionnaire (symptom scales, single item scales, global health scale, and functioning scales) will be calculated with the standard deviation (SD) or interquartile range (IQR). Additionally, a summary score will be calculated based on all scales except financial difficulties and the global quality of life score, to reflect overall quality of life.

A mean score per item with an SD or a median score with a IQR will be calculated for the DTF-QoL questionnaire.

The outcomes of the EQ-5D-5L will be reported as frequency (proportion) of reported problems for each level and for each dimension

#### 8.1.2 Secondary study parameters/endpoints

Patients with DTF will be matched to the general Dutch population using age and sex. The data from the general population in the Netherlands was obtained from the EORTC. The median or mean values for each scale (symptom scales, single items scales, global health scale, and functioning scales) of the EORTC QLQ-C30 (version 3.0) from DTF patients will be compared to the median or mean scores per scale of the general population.

Subgroups will be created based on the information of the baseline questionnaire and will encompass: sex (male, female), age groups (categorized based by the median age and/or quartiles), primary treatment type (surgical resection, systemic treatment, radiotherapy, local treatment (e.g. cryoablation), ethnicity, educational level, relationship status, job demands, comorbidities, tumour location, and tumour recurrences.

Mean or median scores of each scale (EORTC QLQ-C30, version 3.0), items (DTF-QoL, version 1,0) or frequency scores (EQ-5D-5L, version 1,0) will be calculated for each relevant subgroup. More information about these questionnaires can be found in Appendix 1.

The outcomes of the health care utilization and the decision making questionnaires will be descriptive and reported in numbers and corresponding frequencies per answer option. More information about these questionnaires can be found in Appendix 1.

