### **10.2 Secondary study parameter(s)**

Using the baseline values (reported in the baseline questionnaire) for age and sex, patients will be matched, using a 1:10 nearest-neighbour match method, with the general population based on age, and sex using Rstudio (RStudio, version 1.0.153, Boston, MA, package MatchIt).

Differences in scores (of the EORTC QLQ-C30 scales between groups will be tested for their significance using the Mann-Whitney U test or the t-test, depending on the distribution. SPSS Statistics (IBM, Armonk, New York, USA, version 24) will be used for these tests. A two-sided  $p < 0.05$  will be considered statistically significant.

The outcomes of the health care utilization and the decision making questionnaire will be reported in numbers and corresponding percentages per answer option.

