## Appendix 1. Questionnaires

### **Baseline questionnaire, version 1.0, October 29 2019, (Dutch)**

Self-reported demographic data include age, sex, ethnicity, relationship status, family composition, educational level, employment status, physical and mental demands of current job, comorbidities will be collected using this baseline questionnaire. Additionally, clinical data regarding the DTF will be collected: tumour location, multiple DTF locations, received treatments, current treatment, recurrences. Health literacy will be assessed by one single item question (question 14). The baseline questionnaire (A) will be used to identify relevant subgroups (e.g. sex or age).

Outcomes of this questionnaire will be descriptive and are expressed as numbers with corresponding percentages.

Information regarding the pathology, treatment and outcome will be extracted from the (electronic) medical patient records by the researcher on the case report form (CRF). Details about which information is extracted from the (electronic) medical patient records can be found in paragraph 8.1.3. Patients will be made aware of this in the patient information file and will sign informed consent for this on the informed consent form.

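### For the risk-factor objective, age is used only in groups cut at the sample median or quartiles; using age as measured would keep the precision that grouping gives up

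*Combined protocol and SAP*

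**What the plan says.** Secondary objective 2 in section 2 reads "To identify DTF patients who are at risk for late effects and/or impaired HRQoL (risk factors), using the baseline questionnaire", together with the DTF-QoL, the QLQ-C30 and the EQ-5D-5L. Section 8.1.2 carries this out through subgroups. Age enters as "age groups (categorized based by the median age and/or quartiles", one of ten grouping variables. Mean or median scores, or frequencies, "will be calculated for each relevant subgroup". No rule says whether the median, the quartiles or both will be used.

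Appendix 1 confirms that age is available: "Self-reported demographic data include age, sex, ethnicity, relationship status, family composition, educational level". Section 10.2 uses age for a different objective, where "patients will be matched, using a 1:10 nearest-neighbour match method, with the general population"; no age bands are stated there. Section 10.3 derives ages at diagnosis, treatment start and surgery from the medical records, but does not link them to HRQoL. Section 10 gives no model or test relating age to HRQoL among the patients themselves.

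The only sample-size statement is in section 4.4: "Based on the previous response rate we expect to obtain data from 100 DTF patients". Section 1 describes the study as exploratory and hypothesis-generating.

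**The concern.** Grouping a measured variable discards the differences within each group. A median split treats two patients just either side of the cut as different, and two patients decades apart on the same side as alike. If HRQoL changes gradually with age, part of the signal is lost. In a rare disease with about 100 respondents, that loss is not easily made up by recruiting more.

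Two smaller points follow from the same wording. The number of age groups is left open, so it could be settled after the scores by age are known. And a cut at this sample's median depends on who happened to respond, so it does not define an age that another clinic or cohort can use.

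What is at stake is the precision and usefulness of the age result under secondary objective 2. The primary objective does not depend on it.

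**Working it through.** **Inputs from the documents.** About 80 patients under follow-up at the coordinating centre, two further centres of similar size, 250 patients to be approached, and "the response rate of the Dutch patients was 41.5" per cent (all section 4.4). Two-sided 0.05 (section 10.2, stated for the QLQ-C30 between-group tests).

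**Assumptions.** Age is recorded in years. Its effect on a score is linear. The documents give no age distribution, so several shapes are tried.

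**1. The plan's own figure.** 3 × 80 = 240, and 240 × 0.415 = 99.6. With 250 approached, 250 × 0.415 = 103.75. Both agree with about 100 respondents.

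**2. Information kept by grouping.** For a linear effect:

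information kept = between-group variance of age ÷ total variance of age.

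- Median split of a standard normal: the two group means are ±√(2/π), so the share kept is 2/π = 0.637 and the loss is 36.3%.
- Quartile groups of a standard normal: the group means are ±1.271 and ±0.325. The share kept is (1.271² + 0.325²)/2 = (1.615 + 0.106)/2 = 0.861, a loss of 13.9%. This applies if the groups are analysed as a trend.

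| Assumed age shape | Loss, median split | Loss, quartile groups |
|---|---|---|
| Normal | 36.3% | 13.9% |
| Normal (mean 42, SD 14) truncated to 18–85 | 33.9% | 11.7% |
| Right-skewed triangular, 18–80 | 32.4% | 10.2% |
| Uniform, 18–80 | 25.0% | 6.2% |
| Gamma, skewness 1 | 40.6% | 17.4% |

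**3. What this means for an estimate.** With normal age, 100 respondents act like 100 × 0.637 ≈ 64 under a median split. The interval for the age effect widens by √(1/0.637) = 1.25, or 25%. Over the shapes above this runs from √(1/0.750) = 1.15 to √(1/0.594) = 1.30. For a quartile trend with normal age it is √(1/0.861) = 1.08.

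**4. The same loss expressed as power (illustration only).** The correlation that gives 80% power at n = 100 with age as measured is tanh[(1.960 + 0.842)/√97] = 0.277. Simulation with 10,000 runs and normal age gives:

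- age as measured: 80%
- median split: 60%
- quartiles as a trend: 74%
- quartiles as four unordered categories (3 df): 57%

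The effective-sample-size formula gives 60% for the median split, in agreement.

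**5. The open choice.** With no age effect, reporting whichever of the median-split test and the 3-df quartile test has the smaller p-value gives 8.1% error for one outcome, against 5%.

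**The case against.** The strongest reply is that the plan contains no analysis to which power or error rates apply. Section 8.1.2 promises only descriptive scores by subgroup. In section 10.2, the rule that a two-sided p below 0.05 "will be considered statistically significant" follows the matching paragraph and reads as belonging to the comparison with the general population. This stands: steps 4 and 5 are illustrations. Steps 2 and 3 concern precision and apply to description as well as to testing.

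A reader might infer that the wording lets the age cut be tuned to the results. The documents do not support that. Median and quartiles are fixed by the respondents' ages alone, and the wording also allows both to be shown, which involves no selection. The remaining freedom is two groups or four.

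A reader might also infer that a third of the information is lost whichever option is taken. That figure belongs to the median split. Quartiles look worse than a median split only when compared as four unordered categories; as a trend they keep most of the information.

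Finally, age is one of ten subgroup variables, and section 10.2 gives no analysis method for risk factors at all. Changing age alone does not give objective 2 a method. That is true and limits what this change achieves, but it is no reason to coarsen age.

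**Conclusion.** The point holds as a cheap improvement to secondary objective 2. Nothing elsewhere in the documents restores age as measured for that objective. The loss is about 36% for a median split with normal age (25% to 41% over the shapes tried) and about 14% for quartiles used as a trend (6% to 17%). These figures rest on a linear age effect and on assumed age distributions. The open choice of grouping matters little: about 8% instead of 5%, and only if both groupings were tested and one reported.

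It would go too far to say that the study fails a stated power or error rate. It states neither for subgroups, it is exploratory, and no primary result depends on age groups.

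**What to change.** In section 8.1.2, with a matching sentence in section 10.2:

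- Analyse age as a continuous variable for objective 2. For the QLQ-C30 scales, the summary score and the EQ VAS, report the change per 10 years with a 95% CI, using bootstrap or robust intervals where scores are skewed.
- For any DTF-QoL items and EQ-5D dimensions examined, use ordinal regression on continuous age, because a mean slope does not suit responses on 1–4 or 1–5.
- Name one curvature check now, for example a single quadratic term. Report it beside the linear result and do not use it to choose between them. Choosing the better of the linear and the linear-plus-quadratic test would itself raise the error to about 7.3% in simulation.
- Fix one age grouping now, for descriptive tables only.

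No extra patients or questions are needed. The cost is protocol wording, somewhat more analysis in the software already named, and reliance on a linear form, which the curvature check covers.
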